## 2.2 Primary and secondary endpoints

The primary objective of this observational study is to objectify the subjective parameters indicated by the patient (pain, physical impairment, health-related quality of life, activity diary) and the objective parameters measured by the investigator (strength, trunk mobility and trunk fluctuations, sensory, neurodynamics, thickness of the subcutaneous fat layer, muscle fiber alignment and physiotherapeutic objectives).

The secondary objective includes the evaluation of possible relationships between the subjective and objective parameters.

Subjective parameters and their objectification:

- **health-related quality of life**

The health-related quality of life prevailing at the time of measurement is assessed using the German version of the SF-36. The patient fills out the questionnaire independently during the measurement appointment, without being influenced. The examiner adds up the total score achieved and transfers the value to the patient's data sheet.

Objectification of health-related quality of life:

SF-36 Questionnaire, German Version

- **Physical impairment**

The physical impairment prevalent at the time of measurement is assessed using the German version of the Oswestry Disability Questionnaire (ODQ). The patient fills out the questionnaire independently during the measurement appointment, without being influenced. The examiner adds up the total score achieved and transfers the value to the patient's data sheet.

Objectification of physical impairment:

Oswestry Disability Questionnaire, German version

- **Pain**

The pain radiation and the intensity of pain are subjectively assessed by the patient. For this purpose, he is given a sheet with a body chart (pain drawing). With 3 different colors (red = pain, yellow = paresthesia, green = numbness), the patient draws the current sensations at this measurement time. In addition, the patient is surveyed using the visual analogue scale (VAS 0 (no complaints) – 10 (maximum complaints)) to record the intensity of the complaints.

Objectification of radiation area:

The pain drawings are scanned and evaluated with the MATLAB software ([www.ch.mathworks.com](http://www.ch.mathworks.com)). Here, the radiation area is quantified as a percentage of the total body surface.

Objectification intensity:

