### - **Force**

The maximum isometric force and the force development of the muscles supplied by the affected spinal nerve are tested in a standardized starting position. For this purpose, a dynamometer held by hand by the tester is used. The patient is asked to press against the examiner's hand as hard and as long as possible. In addition, a superficial electromyography is performed, in which the electrodes are glued to the points provided for this purpose on the skin. To ensure that the test situation remains isometric, the examiner applies exactly as much force as the patient is willing to deploy. The test is carried out 3 times in a row with a 30-second break. The values are transferred to the data sheet. The measurements take place on both sides, starting with the subjectively weaker side.

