### - **Sensors**

The sensory system of the affected area (segmentally associated dermatome) is tested directly on the skin in the radiation area. The results are transferred to the data sheet. The pain threshold is raised on a Valleix point along the iliac crest. Measurements are always taken at the same measuring points, on the affected side.

Objectification of sensor technology:

The pressure sensation is recorded by means of a monofilament, the 2-point discrimination with the Greulich star, the sense of vibration with the tuning fork (according to Rydel-Seiffer), the muscle reflex with the reflex hammer in a left/right comparison including acceleration measurement (accelerometer MSR165, [www.msr.ch](http://www.msr.ch)) and the pain threshold with the algometer (NOD, [www.to-nod.com](http://www.to-nod.com)).

- **Neurodynamics**

The neurodynamics of the affected spinal nerve are tested using the appropriate pain provocation test. For this purpose, a hydrogoniometer is required, with which the exact number of degrees at which the symptoms are triggered is measured. The number of degrees is transferred to the data sheet. The tests are carried out in a standardised manner. If the spinal nerve L2/L3 is affected, the crossed Lasègue test is performed, and for L4/L5/S1 the Lasègue test.

Objectification of neurodynamics:

Hydrogoniometer

- **Subcutaneous fat tissue and muscle fiber alignment**

The thickness of the subcutaneous fatty tissue is measured on the rectus femoris muscle, 10 cm above the patellar base, and on the medial gastrocnemius muscle at the level of the largest calf circumference, in both legs.

Objectification Thickness Subcutaneous Fat Tissue and Muscle Fiber Alignment:

The portable ultrasound device from Telemed ([www.pcultrasound.com](http://www.pcultrasound.com)) is used for this purpose. The images are evaluated with the Osirix ([www.osirix-viewer.com](http://www.osirix-viewer.com)) software and the number of millimetres, fat thickness and muscle fibre degree angle are transferred to the data sheet.

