**Overview of the measurement process**

Expiration	Data collection	Instrument	Time exposure
- Questionnaire	subjective health-related quality of life	SF-36 Questionnaire	5 min
- Questionnaire	subjective physical impairment	ODQ	5 min
- Pain Evaluation	subjective pain radiation and intensity	VAS	5 min
- Demography	Height, body weight, body fat percentage	Pain Drawings Stadiometer, Tanita – Scale	5 min
- Ultrasound measurement of the rectus femoris and gastrocnemius medialis muscles	Thickness of subcutaneous fatty tissue, alignment of muscle fibers, bilateral	Portable Ultrasound Machine (TeleMed)	10 min
- Trunk mobility	Mobility of the spine in flexion, extension, lateral flexion	Sway Star™	2 min
- Hull swaying	Torso movements during 30 s – one-leg stand, both sides	Sway Star™	2 min
- Hull swaying	Trunk Movement during 8m - Walking	Sway Star™	5 min
- Neurodynamics	Pain provocation test, bilateral	Hydrogoniometer	2 min
- Evaluation of the sensor technology	Sensation of pressure, 2-point discrimination, sense of vibration, muscle reflex, pain threshold bilateral	Monofilament, Greulich Star, Neurological Tuning Fork, Reflex Hammer, Accelerometer, NOD Algometer	10 min
- Force measurement	maximum isometric force, force development, bilateral	NOD – isometric load cell, surface electromyography	5 min

The maximum time required per measurement appointment is one hour. With 6 measurement points, the time required adds up to 6 hours and extends over 8 months.

In addition, the patient keeps an activity diary at home and logs the painkiller intake, which takes about 5 minutes a day.

The treating physiotherapist records the content of all therapy sessions. The protocol to be used for this purpose is explained and instructed to the physiotherapist by the investigators at the beginning of the study. The documentation of physiotherapeutic treatment is one of the duties of a physiotherapist, so there is no additional effort for him. All he has to do is use the protocol template. Furthermore, the treating physiotherapists are asked to continue their usual interventions and treatments regardless of the study participation of their patients.

The following biases could occur:

- Sociodemographic and personal characteristics of the subjects: men/women, age
- Duration of back pain
- Truthful keeping of the activity diary and painkiller intake log
- physiotherapeutic treatment

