# **7 QUALITY CONTROL AND DATA PROTECTION**

## **7.1 Quality measures**

The measurements and surveys are carried out exclusively by trained personnel. The examiners who carry out the measurements and interviews are trained physiotherapists with experience in dealing with back patients. Patient recruitment is carried out by the head of the study, [name] will take place.

For quality assurance, the Ethics Committee may visit the research sites. Direct access to the source data and all project related files and documents must be granted on such occasions.

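### Nothing keeps the examiner from knowing the SF-36, ODQ and VAS results before the hand-held force and symptom-onset angle tests, so examiner expectation could distort the planned subjective-objective correlations

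*Combined protocol and SAP*

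**What the plan says.** All references are to the combined protocol and SAP.

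- **Scoring (section 2.2).** For the SF-36 and again for the ODQ: "The examiner adds up the total score achieved and transfers the value" to the data sheet.
- **Timing (section 2.2).** For both questionnaires: "The patient fills out the questionnaire independently during the measurement appointment, without being influenced". The VAS and the pain drawing also describe the state at the time of measurement.
- **Force (section 2.2, Force).** For this test "a dynamometer held by hand by the tester is used", and, to keep the contraction isometric, "the examiner applies exactly as much force as the patient is willing to deploy". The starting position is standardised, there are three repeats, and the device records the result.
- **Angle (section 2.2, Neurodynamics).** The provocation test uses a hydrogoniometer, "with which the exact number of degrees at which the symptoms are triggered is measured".
- **Staff (section 7.1).** "The examiners who carry out the measurements and interviews are trained physiotherapists with experience in dealing with back patients".
- **Order (section 3.3).** The overview table puts SF-36, ODQ (entered as "subjective physical impairment") and pain evaluation at the top. Neurodynamics, sensory testing and force come last.
- **Use of the data (sections 2.1, 2.2, 4.1).** Relating subjective to objective parameters is the secondary objective. Pain with strength, and ODQ/SF-36 with strength, are listed hypotheses. Neurodynamics is in no hypothesis pair, but section 4.1 includes it among the objective parameters to be correlated with the subjective ones.
- **Biases (section 3.3).** The list covers personal characteristics, duration of pain, truthful diary keeping and physiotherapy. Examiner expectation is not on it. No section provides for masking, a separate scorer, or scoring after the physical tests.

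**The concern.** A correlation between a self-reported score and a physical measurement can be read as an association in the patient only if the measurement was taken independently of the score. Here the person taking the measurement may know the score. An examiner who has just totalled a poor ODQ could brace less firmly, encourage less, or end a provocation test sooner. Any of these would tie the two variables together through the examiner, and neither a Pearson nor a Spearman coefficient can separate that tie from a real association.

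At stake are the correlations of pain and of ODQ/SF-36 with strength, and the correlations with the symptom-onset angle that section 4.1 adds. Measures recorded mainly by instrument (trunk sway, ultrasound, surface EMG) are less exposed. Hypotheses that relate one objective measure to another do not use the scores at all.

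**Working it through.** **1. Can the examiner know the scores before testing?** Reading the sections together:

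| Step | What the document supports |
|---|---|
| Examiner handles SF-36 and ODQ totals | Stated (2.2) |
| Questionnaires completed at the same appointment as the tests | Stated (2.2) |
| Same group of staff interviews and measures | Stated (7.1) |
| Questionnaires listed before the physical tests | Stated as a listing (3.3); not said to be binding |
| Totals calculated before the physical tests | Not stated |
| One examiner does both tasks at a given visit | Not stated |
| Anything that prevents either of the last two | None found |

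The route is open rather than prescribed. With six visits per patient (3.3), an examiner who scored an earlier visit may also remember those totals later, whatever the order within a visit.

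**2. The plan's own sample size.** Inputs from section 4.1: two-sided alpha 0.05, r = 0.5, power 0.95. With the point-biserial model in G\*Power,

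ncp = sqrt(N) × r / sqrt(1 − r²), df = N − 2.

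At N = 42, ncp = 6.481 × 0.5 / 0.866 = 3.742 and power = 0.9545. At N = 41, power is 0.94995, just short of 0.95. The stated 42 is reproduced and is used below.

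**3. Critical correlation at n = 42.** With t(0.975; 40) = 2.021,

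|r| critical = 2.021 / sqrt(40 + 2.021²) = 0.304.

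**4. Illustration of size.** Assumption, not in the documents: the true correlation is 0, and knowledge of the score explains a share s of the variance of the force reading. The induced correlation is then r = sqrt(s). The rejection rate was simulated for bivariate normal data at n = 42. The last column is a hand check with Fisher's z: the shift is atanh(r) × sqrt(39), and the rate is P(Z > 1.96 − shift) + P(Z < −1.96 − shift).

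| Assumed share s | Induced r | Simulated rejection | Shift | Fisher z check |
|---|---|---|---|---|
| 0% | 0 | 5.0% | 0 | 5.0% |
| 1% | 0.100 | 9.7% | 0.627 | 9.6% |
| 2% | 0.141 | 14.6% | 0.889 | 14.4% |
| 5% | 0.224 | 29.9% | 1.420 | 29.5% |

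Rounded, this is 10%, 15% and 30% against a nominal 5%. The test is two-sided, so with a true r of 0 these rates do not depend on the sign of the examiner effect.

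**5. When the true correlation is not 0.** If the examiner effect has the same sign as the true association, the expected r grows. For example, take a true r of 0.3 and an assumed shift of 0.1 SD of the force reading per SD of the score. The expected r is then (0.3 + 0.1) / sqrt((0.3 + 0.1)² + 1 − 0.3²) = 0.4 / sqrt(1.07) = 0.39. With a small shift of the opposite sign, r would move towards zero.

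**The case against.** The other side has several good points.

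- **The patient's effort drives the force reading.** The protocol has the examiner match the patient's force, from a standardised position, with three repeats and electronic recording. A reader might infer that the examiner's resistance sets the value; the Force text does not say that. What remains is that counter-force and encouragement still pass through a device the examiner holds. Electronic recording removes reading error, not that influence.
- **The sequence is inferred.** A reader might take it as fact that one examiner totals the scores and then tests. No section fixes when totals are calculated or says that one person does both at a visit. The point therefore rests on the absence of any safeguard.
- **Direction is unknown.** A reader might conclude that the bias must inflate correlations. That holds if expectation runs in the direction of the true association, or if the true r is 0. The documents do not establish either.
- **The variance shares are arbitrary.** They show how sensitive the test is if a bias exists, not that one exists.
- **Scope is limited.** Only the correlations with strength are formal hypotheses among those at issue. The angle enters through the general list in 4.1, and symptom onset is partly the patient's own report.
- **Full masking is impossible.** The examiner needs the affected root to choose the provocation test and the muscles, starts with the subjectively weaker side, and tests sensation in the radiation area. Sealing every subjective record would conflict with that last step. This objection stands and shapes the fix.

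Self-completion without influence is not an answer, because it protects the patient's responses and not the examiner's later measurements.

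**Conclusion.** The point holds in a limited form. The plan leaves the examiner free to know the SF-36, ODQ and VAS results before taking examiner-dependent measurements that will be correlated with them, and it does not list this among its possible biases. The exposure concerns strength against pain and ODQ/SF-36, and the symptom-onset angle through the general list in 4.1. It does not extend to the study as a whole.

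Neither size nor direction can be obtained from the documents. The rejection rates of about 10%, 15% and 30% rest entirely on assumed shares of 1%, 2% and 5% and a true correlation of 0. They show only that a small examiner effect would be enough to matter at n = 42. This is worth changing because the remedy is almost free, not because a bias has been demonstrated. The sample size is unaffected.

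**What to change.** In sections 2.2 and 3.3, state that:

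1. the patient completes the SF-36, ODQ and VAS on paper and closes them in an envelope;
2. the envelope is opened and the forms are scored only after the last physical test of that visit;
3. totals from earlier visits are kept off the data sheet in use;
4. where another trained examiner already on the study is available, that person does the scoring.

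Do not seal the pain drawing unless the sensory test site is already fixed, because sensory testing takes place in the radiation area. In section 3.3, add examiner expectation to the list of possible biases.

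**Cost.** A few sentences and one envelope per visit, with no additional staff and no change to n = 42. The VAS would have to be self-completed on paper; the present text only says that the patient is surveyed with it.

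**Downside.** Masking remains partial, because the examiner still knows the affected side and root and may recall earlier visits. Missing questionnaire items would be noticed only at the end of the visit, so the forms should be checked for completeness before the patient leaves.

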#### Pain Drawing (VAS)

---

H0 There is no correlation between pain and physical impairment and health-related quality of life.  
H1 There is a correlation between pain and physical impairment and health-related quality of life.

H0 There is no correlation between pain and activity diary.  
H1 There is a correlation between pain and activity diary.

H0 There is no correlation between pain and strength and muscle fiber alignment.  
H1 There is a correlation between pain and strength and muscle fiber alignment.

H0 There is no correlation between pain and trunk mobility and trunk fluctuations.  
H1 There is a correlation between pain and trunk mobility and trunk fluctuations.

H0 There is no correlation between pain and sensory activity.  
H1 There is a correlation between pain and sensory activity.

---

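### The VAS under Pain is anchored on complaints, and no rule says which drawing colours count, so the pain hypotheses may not isolate pain

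*Combined protocol and SAP*

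**What the plan says.** Section 2.2, under Pain, opens with the construct: "The pain radiation and the intensity of pain are subjectively assessed by the patient". Two measures follow.

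- **Drawing.** "With 3 different colors (red = pain, yellow = paresthesia, green = numbness), the patient draws the current sensations" on a body chart. The chart is scanned and processed in MATLAB, where "the radiation area is quantified as a percentage of the total body surface". No colour rule is given.
- **VAS.** The scale is used "to record the intensity of the complaints", with its two ends given as "VAS 0 (no complaints) – 10 (maximum complaints".

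The measurement overview in section 3.3 lists both instruments under "subjective pain radiation and intensity". Sections 2.1 and 4.1 then state five pain hypotheses under the heading Pain Drawing (VAS), among them the null hypothesis "There is no correlation between pain and sensory activity". Neither section says whether pain means the area or the VAS, or which colours enter the area.

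Section 2.2, under Sensors, places the sensory testing on the skin of the radiation area. The pain threshold is the exception: it is taken at a point along the iliac crest. The reflex is a left/right comparison.

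**The concern.** The stated target is pain, but neither measure is tied to pain alone. Section 1 counts sensory disturbances among the symptoms of back patients, so a patient with marked numbness and little pain could properly give a high complaints rating. Such a rating cannot later be divided into pain and other symptoms, and it would be taken at all six visits.

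For the drawing, three sensations are recorded but one area is named. An analyst could compute it from red only, from each colour, or from all colours, and each choice would comply with the plan. That leaves the definition of a leading variable open until the data have been seen.

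The hypothesis on pain and sensory function has most to lose. If yellow and green count, self-reported paresthesia and numbness enter the pain side, while monofilament, two-point discrimination and vibration results from the same region stand on the other side. A significant result could then reflect sensory symptoms agreeing with sensory tests, and be reported as a finding about pain.

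**Working it through.** **1. The plan's own figure.** Section 4.1 gives n = 42 for a correlation of 0.5, two-sided alpha 0.05 and power 0.95. With a noncentral t, noncentrality √n × r / √(1 − r²) and n − 2 degrees of freedom, power is 0.9545 at n = 42 and 0.94995 at n = 41. So 42 is reproduced. If both variables are treated as bivariate normal, simulated power at n = 42 is about 0.935; that model is used below. The present point does not change the stated n.

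**2. The VAS.** No arithmetic applies. The opening sentence of the paragraph and the overview table name pain intensity; the purpose and the anchors name complaints. These are different quantities in a population whose symptoms include sensory disturbance.

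**3. The area, if all colours were pooled.** Nothing in this step comes from the documents except n = 42 and alpha = 0.05. Let the area be A = P + N, with P the pain part and N the paresthesia and numbness part, the two uncorrelated. Let s = Var(N)/Var(A), let N correlate c with a sensory test T, and let P be unrelated to T. Then

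Corr(A, T) = c × SD(N)/SD(A) = c × √s.

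For example, s = 0.25 and c = 0.5 give 0.5 × 0.5 = 0.25. Each cell shows the induced correlation and the simulated chance of a two-sided p < 0.05 at n = 42:

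| s | c = 0.3 | c = 0.5 | c = 0.7 |
|---|---|---|---|
| 0.10 | 0.095; 9% | 0.158; 17% | 0.221; 30% |
| 0.25 | 0.150; 16% | 0.250; 36% | 0.350; 64% |
| 0.50 | 0.212; 27% | 0.354; 65% | 0.495; 93% |

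The nominal rate is 5%.

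**4. The opposite error.** Suppose P correlates 0.5 with some other measure that is unrelated to N. The pooled area then shows 0.5 × √(1 − s), which is 0.474, 0.433 and 0.354 for s = 0.10, 0.25 and 0.50. Power at n = 42 falls from about 0.935 to 0.905, 0.836 and 0.643. This is how the other pain hypotheses could be affected, again only under pooling.

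**The case against.** The strongest reply is that pooling appears nowhere in the documents. Red is assigned to pain, the paragraph opens by naming pain radiation, and a red-only reading fits the text as well as an all-colour one. The scans keep the colours, so nothing about the area is lost before analysis. This stands: for the area, the defect is a missing rule.

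Second, the English reads as a translation (section 2.2 calls sensory testing Sensors), so the word complaints may not match the form that patients see. That is possible, and it would reduce the VAS point to a correction of the protocol text. The documents do not settle it, and the anchors as written conflict with the stated target.

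Third, overlap with the sensory tests is partial. It reaches monofilament, two-point discrimination and vibration, but not the iliac-crest pain threshold and not, in any direct way, the reflex. A drawn extent is also a different quantity from a measured threshold, and relating the two is a declared secondary objective. So a correlation caused by the yellow and green areas would be mislabelled rather than meaningless. This too stands, and it confines the false-positive argument to one of the five pain hypotheses.

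Fourth, every rate above depends on assumed values. That is correct, and it is why a range is given and no single figure.

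**Conclusion.** The plan does not define pain tightly enough for its pain hypotheses. The VAS is the firmer part: its written anchors are wider than the stated construct, and data collected under them cannot be separated. For the area, the plan leaves open which colours count, so the variable may include non-pain sensations.

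A reader might infer that the plan merges the three colours and that its pain hypotheses therefore do not test pain. The documents do not support that. They never say the colours are combined, they name pain as the target, and they keep the information needed for a red-only area. What they support is that the hypotheses may not test pain specifically.

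The size cannot be fixed from the documents. If the colours were pooled and pain were unrelated to the sensory tests, the chance of a spurious pain-sensory finding at n = 42 would run from about 9% (s = 0.10, c = 0.3) to about 93% (s = 0.50, c = 0.7). That range illustrates the area only; it does not quantify the VAS problem.

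**What to change.** In section 2.2:

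- Anchor the VAS to pain, with 0 as no pain and 10 as maximum pain, and check that the German form says the same.
- Have the MATLAB evaluation output the area separately by colour.
- Define the pain area as red alone, and report the yellow and green areas as separate variables.

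In section 4.1, state for each of the five pain hypotheses whether it uses the red area or the VAS.

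The cost is a colour filter in an evaluation that is already planned, and changed anchor wording. Separate VAS lines for paresthesia and numbness are optional and not part of the correction. The anchors need to be settled before ratings are collected; the colour rule can be added at any time before analysis.
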